3 STUDY DESIGN

An open-label, intervention pilot-study in 15 healthy human volunteers. In this pilot study, we will enrol 10 subjects who will take Beta-glucan daily for seven days, and 5 subjects who will serve as control group and do not have to take Beta-glucan but who will be analyzed at the same time points as the subjects in the Beta-glucan group.

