7 METHODS

7.1 Study parameters/endpoints

7.1.1 Main study parameter/endpoints

The primary objective of the study is to evaluate the systemic effects of orally administered Beta-glucan on innate immune responses of leukocytes. The effects of Beta-glucan will be determined by measuring the *ex-vivo* responsiveness of leukocytes to various inflammatory stimuli as a marker for the antimicrobial response. The primary outcome measure is the TNF- α secretion by *ex vivo* LPS-stimulated peripheral blood mononuclear cells (PBMC's).

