7.1.3 Other study parameters Not applicable

7.2 Randomisation, blinding and treatment allocation

We will use a open-label design in which subjects will be randomized to the Beta-glucan or control group by the opening of sealed envelopes.

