7.3.1 Time course

Baseline Evaluation (day 0):

• 2 faecal samples collected within 48 hours prior to Beta-glucan intake for analysis of microbiota. Blood sampling prior to Beta-glucan intake for immunological analysis (cytokine production of leukocytes stimulated *ex vivo* with various stimuli), for analysis of peripheral blood mRNA expression of genes related to the immune response, epigenetic modifications, levels of Beta-glucan, and phagocytosis and killing of *C. albicans*.

3 hours after the first Beta-glucan intake (day 0 + 3 hours):

• Blood sampling for immunological analysis (cytokine production of leukocytes stimulated *ex vivo* with various stimuli), for analysis of peripheral blood mRNA expression of genes related to the immune response, and levels of Beta-glucan.

6 hours after the first Beta-glucan intake (day 0 + 6 hours):

• Blood sampling for immunological analysis (cytokine production of leukocytes stimulated *ex vivo* with various stimuli), for analysis of peripheral blood mRNA expression of genes related to the immune response and levels of Beta-glucan.

24 hours after the first Beta-glucan intake (day 1):

• Blood sampling for immunological analysis (cytokine production of leukocytes stimulated *ex vivo* with various stimuli), for analysis of peripheral blood mRNA expression of genes related to the immune response and levels of Beta-glucan.

Days 0-5:

• Daily intake of 1000mg Beta-glucan

Day 6:

- 1 faecal sample collected within 24 hours prior to the last Beta-glucan intake for analysis of microbiota. Blood sampling prior to the last Beta-glucan intake for immunological analysis (cytokine production of leukocytes stimulated *ex vivo* with various stimuli), for analysis of peripheral blood mRNA expression of genes related to the immune response, epigenetic modifications, levels of Beta-glucan, and phagocytosis and killing of *C. albicans*.
- Registration of any adverse experience. This includes any intercurrent illness that may arise during therapy.

3 hours after the last Beta-glucan intake (day 6 + 3 hours):

• Blood sampling for immunological analysis (cytokine production of leukocytes stimulated *ex vivo* with various stimuli), for analysis of peripheral blood mRNA expression of genes related to the immune response, levels of Beta-glucan.

6 hours after the last Beta-glucan intake (day 6 + 6 hours):

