7.3.2 Laboratory tests

Immunological sampling

- Time-points: days 0, 0+3hrs, 0+6hrs, 6, 6+3hrs, 6+6hrs, and 21
- Parameters to be tested:
 - Ex-vivo cytokine production;
 - After 24h stimulation, determination of TNF-α, IFN-1, IL-6, IL-1β.
 - After 48h stimulation, determination of IL-10, IFN-γ
 - After 7 day stimulation, determination of IL-17 and IL-22
 - Method: PBMC and monocyte stimulation. Stimuli to be used: RPMI (control stimuli), LPS, Pam3Cys, Poly(I:C), C. albicans, staphylococcus aureus, and mycobacterium tuberculosis.
 - o Peripheral blood mRNA expression of genes related to the immune response
 - Peripheral blood levels of Beta-glucan
 - Epigenetic modifications
 - phagocytosis and killing of *C. Albicans*
 - Faecal microbiota
- Total amount of blood needed: 360ml (45 ml on 8 different timepoints)
 - o 40 ml EDTA-anticoagulated blood for stimulation experiments, phagocytosis/killing, and epigenetic analysis.
 - 2.5 ml collected directly into a PAXGene[®] Blood RNA tubes (PreAnalytix). These tubes are used to prevent any post-sampling stimulation and to ensure RNA integrity after storage. The reagents used in these BD VacutainerTM tubes allow immediate nucleic acid precipitation and nuclease inhibition. After collection and RNA stabilization at room temperature (4 hours), samples are stored at -20°C until RNA extraction.
 - o 2 ml heparin anticoagulated blood for determination of Beta-glucan by ELISA

In order to take into account the value of the biological samples obtained during this study, all leftovers will be stored in a biobank at the end of the study. This includes (if available) whole

blood, serum, plasma, RNA for the duration of 5 years. Those samples will be secondarily used for research in the field of sepsis or related pathologies. Each participant in the study will be appropriately informed and will have the right to refuse the storage of his/her own samples.

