8.2 Descriptive statistics

For the descriptive statistics, values will be given as mean \pm SD or median and ranges, depending on their distribution. For comparisons, paired Students t -tests or Willcoxon-tests for parametric and nonparametric data as appropriate will be used. Changes over time will be analysed using ANOVA repeated measures. A p value <0.05 is considered significant. Statistical analyses will be performed with SPSS 16.0 (SPSS, Chicago, IL) software.

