8.3 Multivariate analysis

Not applicable.

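### The day-0 TNF-alpha value is collected in every subject, but the methods stated in Section 8.2 never use it as a covariate, which gives up some precision in a 10 v 5 randomised comparison

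*Protocol*

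**What the plan says.** Protocol Section 7.1.1 gives the outcome: "The primary outcome measure is the TNF- α secretion by" LPS-stimulated mononuclear cells ex vivo. Section 3 sets the size: "we will enrol 10 subjects who will take Beta-glucan daily for seven days, and 5 subjects who will serve as control group". Section 7.2 makes the comparison randomised: "subjects will be randomized to the Beta-glucan or control group by the opening of sealed envelopes".

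Section 7.3.1 schedules, on day 0, "Blood sampling prior to Beta-glucan intake for immunological analysis". Section 3 adds that the controls are subjects "who will be analyzed at the same time points as the subjects in the Beta-glucan group", so all 15 subjects should have a pre-intake value. Section 7.3.2 counts "45 ml on 8 different timepoints": one before intake and seven after it. The time-point list in 7.3.2 leaves out the 24-hour sample, but 7.3, 7.3.1 and 7.3.3 include it.

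For analysis, Section 8.2 names paired t-tests or Wilcoxon tests for comparisons, and then: "Changes over time will be analysed using ANOVA repeated measures". The significance threshold is p < 0.05. Section 8.3, on multivariate analysis, reads "Not applicable". No section names a baseline covariate.

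**The concern.** Because the arms are randomised, the pre-intake value has the same expectation in both, and adjusting for it is a valid way to reduce the error variance of the arm difference. The named methods do not use it that way. A paired test subtracts it. A repeated-measures ANOVA treats it as one more level of the outcome, and with an arm factor and only two time points that ANOVA is a comparison of change scores. Subtraction gives baseline a fixed weight of 1, whatever its correlation with the later value, and over-corrects when that correlation is modest.

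This matters more than usual here because the trial is so small. With 10 and 5 subjects, the between-arm difference in mean baseline has a standard deviation of √(1/10 + 1/5) = 0.55 outcome SD by chance alone. At stake is precision on the primary outcome, not validity.

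**Working it through.** **Nothing to reproduce.** Section 4.4 declines a power calculation, and the protocol gives no SD, effect size or correlation.

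**Inputs.** From the protocol: n = 10 and 5 (Section 3), significance at 0.05 (Section 8.2). Assumed: two-sided testing, normal outcome with equal SD at each time, effect 1 SD (1.5 SD as a check), rho from 0.3 to 0.9. The comparator is a between-arm change score, which is what the stated ANOVA becomes with an arm factor and two time points. Section 8.2 does not itself mention an arm factor.

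**Formulas, one post-dose time point, SD = 1.** Let h = 1/10 + 1/5 = 0.30.

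- Change score: variance of the arm difference = 2(1 − rho)·h, on 13 df.
- ANCOVA: variance = (1 − rho²)·h, times 12/11 on average for chance baseline imbalance at N = 15, on 12 df.
- Large-sample ratio, ANCOVA to change score: (1 + rho)/2.

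Example at rho 0.5, effect 1 SD. The change-score variance is 2 × 0.5 × 0.30 = 0.300, SE 0.548, noncentrality 1.83, power 39%. The ANCOVA variance is 0.75 × 0.30 × 12/11 = 0.245, SE 0.495, noncentrality about 2.02, power 46%.

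Power for a 1 SD effect (noncentral t; ANCOVA averaged over the chance imbalance):

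| rho | variance ratio | ratio × 12/11 | change score | ANCOVA | difference |
|---|---|---|---|---|---|
| 0.3 | 0.65 | 0.71 | 29.8% | 39.6% | +9.8 |
| 0.5 | 0.75 | 0.82 | 39.4% | 46.3% | +6.9 |
| 0.7 | 0.85 | 0.93 | 58.8% | 61.8% | +3.0 |
| 0.8 | 0.90 | 0.98 | 76.1% | 76.5% | +0.4 |
| 0.9 | 0.95 | 1.04 | 96.5% | 95.5% | −1.0 |

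At 1.5 SD the pairs are 57% and 72% (rho 0.3), 72% and 80% (0.5), 90% and 92% (0.7). Simulation gave the same picture, with type I error near 5% for every between-arm test.

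**All eight samples.** Assume equal correlations and a constant 1 SD effect at all seven post-dose times. To isolate the covariate, both analyses must use the same post-dose mean, whose variance is (1 + 6rho)/7.

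- Change of the mean: variance (1 + 6rho)/7 + 1 − 2rho, which is 0.571 at rho 0.5 and 0.343 at 0.7. Power 61% and 82%.
- ANCOVA of the mean: residual variance (1 + 6rho)/7 − rho², which is 0.321 and 0.253. Power 81% and 89%.

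So the covariate alone adds 20 points at rho 0.5 and 7 at rho 0.7, if the effect really is constant.

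**The case against.** **A larger loss might be inferred.** Under the constant-effect set-up at rho 0.5, the 7-df group-by-time test has 34% power and baseline-adjusted analysis of the post-dose mean has 81%. Reading that 47-point gap as the price of omitting the covariate would be wrong. Of it, 61 − 34 = 27 points come from replacing a 7-df test with a single averaged contrast, before any covariate enters. Nor does the protocol assume a constant effect: Section 7.3 asks separately about immediate effects on day 0, an additive effect after seven days, and prolonged effects at three weeks. Suppose the effect is 1.5 SD at 3 and 6 hours only, or 1 SD at the three day-6 samples only. The post-dose average is then 3/7 = 0.43 SD in either case. At rho 0.5 the averaged ANCOVA has 23% power, against 94% and 69% for group-by-time. The figure of 81% is no argument for the covariate, and averaging should not be imposed.

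**Section 8.3 might be read as a ban on covariates.** It is not one. The entry "Not applicable" stands under multivariate analysis and says nothing explicit about baseline adjustment.

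**The stated methods might be called invalid or underpowered.** Change-score and repeated-measures comparisons between randomised arms hold their type I error. Within-arm paired tests do not lack nominal power (about 80% in the treated arm at 1 SD, rho 0.5). Their weakness is that they ignore the controls, which is a different matter.

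**It is a pilot, and covariates are often left to the SAP.** This is the strongest objection, and part of it stands: the synopsis calls the analysis descriptive, the gain is modest, and hours-apart samples from one person may be highly correlated, in which case there is no gain. But Section 8.2 does not leave the method open. It names tests, a threshold and software, and Section 7.5 replaces withdrawals in order to keep power. The remark concerns a stated choice, not a missing detail.

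**Conclusion.** The point holds as a matter of efficiency. A baseline that is already collected in both randomised arms is used only as a pair or an outcome level. Using it as a covariate at a single time point is worth about 10, 7 and 3 power points at rho 0.3, 0.5 and 0.7 for a 1 SD effect. It is worth nothing at 0.8 and costs about 1 point at 0.9.

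These figures rest on assumed rho and effect size, normality, and a change score as comparator. The gain at low rho is over subtraction: at rho 0.3 an unadjusted post-dose comparison does as well as ANCOVA (both about 39%). The case for the covariate is therefore that it stays close to the better of the two simple analyses without rho having to be known. The larger gain on the post-dose mean depends also on a constant effect, which the protocol gives no reason to assume.

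**What to change.** In Section 8.2, state that the arms are compared on TNF-alpha at each post-dose time point of interest, with the day-0 pre-intake value as covariate. Time points matching the questions in Section 7.3 would be, for example, day 0 + 3 and 6 hours, day 6 and day 21. Use ANCOVA per time point, or a mixed model that keeps time-specific arm effects and does not force one post-dose average.

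Apply the same rule to the other scalar outcomes with a day-0 value, such as the other cytokines and the killing assay. For scalar faecal measures, use the mean of the two baseline samples as covariate; this does not carry over directly to microbiota composition, which is not a scalar. Keep the paired tests as within-arm description. A clause in Section 8.3 saying that baseline adjustment is not excluded would prevent a misreading.

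The cost is a sentence or two, one more model term and one residual degree of freedom (13 to 12), with a loss of about 1 power point if rho is near 0.9. No new data are needed. Which time point carries the primary test is a separate decision that this change does not settle.

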7.3 Study procedures

Healthy volunteers who meet all inclusion criteria, none of the exclusion criteria and have given informed consent to participate in the study will be randomized to the Beta-glucan or the control group. The subjects in the Beta-glucan group will take Beta-glucan 1000 mg daily for 7 days, the subjects in the control group won't have to take Beta-glucan but will otherwise follow the same timecourse as the Beta-glucan treated subjects. Before, and 3, 6, and 24 hours after the first Beta-glucan ingestion (day 0), before, and 3 and 6 hours after the 7th ingestion of Beta-glucan (day 6), and on day 21 subjects have to come to the research room of the intensive care research unit for blood sampling (see appendix 1 for flowchart). On the first day of Beta-glucan ingestion we want to determine the immediate effects of oral Beta-glucan on leukocyte function, and if possible establish a plasma concentration – response curve. After 7 days of Beta-glucan ingestion we want to do the same measurements to determine

whether there is an additive effect of repetitive Beta-glucan intake. After 3 weeks we want to determine whether short-term intake of Beta-glucan results in prolonged immunological effects. Before the first intake of Beta-glucan subjects have to hand in 2 faecal samples collected within 48 hours prior to Beta-glucan intake, and one faecal sample collected within 24 hours prior to days 6 and 21. Throughout the studyperiod, subjects will document their consumption of Beta-glucan containing foods in an "eat-diary" (Appendix 2), with a maximalization of the amount of consumed Beta-glucan containing foods in order to minimize the inter-variability caused by variation in diet (Appendix 2).

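### Section 8.2 names no comparison with the randomised controls, and its repeated-measures ANOVA loses every subject with one missed sample

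*Protocol*

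**What the plan says.** Section 3 describes the trial as "An open-label, intervention pilot-study in 15 healthy human volunteers", and continues: "we will enrol 10 subjects who will take Beta-glucan daily for seven days, and 5 subjects who will serve as control group". It adds that the controls are analysed at the same time points as the treated subjects. Section 7.2 says that allocation is randomised by sealed envelope.

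Section 8.2 is the whole analysis text. For comparisons it gives paired t-tests or Wilcoxon tests, depending on the distribution. For the time course: "Changes over time will be analysed using ANOVA repeated measures". The threshold is "A p value <0.05 is considered significant" and the software is fixed: "Statistical analyses will be performed with SPSS 16.0 (SPSS, Chicago, IL) software". The section names no arm term, no arm-by-time term, no rule for a missed sample and no sphericity correction.

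Section 7.3 sets the blood sampling: "Before, and 3, 6, and 24 hours after the first Beta-glucan ingestion (day 0), before, and 3 and 6 hours after the 7th ingestion", and again on day 21. That makes eight samples. Section 7.3.2 agrees on the number of draws, "Total amount of blood needed: 360ml (45 ml on 8 different timepoints", but its list for immunological sampling has seven entries: "Time-points: days 0, 0+3hrs, 0+6hrs, 6, 6+3hrs, 6+6hrs, and 21". The 24-hour sample is absent from that list, although section 7.3.1 assigns cytokine stimulation to it.

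Section 7.5 replaces subjects after withdrawal or exclusion, up to ten. It does not mention a subject who stays in the trial but lacks one sample.

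**The concern.** Two features of section 8.2 weaken the trial's ability to answer its own question.

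- **The controls have no stated role in the analysis.** A paired test and a test of change over time are both within-subject. Ex vivo TNF-α can move over three weeks for reasons shared by both arms, such as time of day, assay batch, repeated sampling or the limit on Beta-glucan-containing food in section 7.3. Only a comparison of change between arms separates such drift from an effect of the product. Running the paired test in each arm and contrasting the two p-values does not do this, because the arm of five is less likely to reach significance at the same size of change.
- **The named method uses only complete subjects.** One failed culture or missed draw removes that subject's other seven values. With 10 and 5 subjects, each loss counts.

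At stake is whether a p-value below 0.05 from this pilot can be read as evidence about Beta-glucan, and how many of the 15 subjects contribute to it.

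**Working it through.** The protocol states no power, effect size, correlation or missing rate, so it has no figure of its own to reproduce.

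**Inputs.** 10 treated and 5 control subjects (section 3). Eight samples at 0, 3, 6, 24, 144, 147, 150 and 504 hours (section 7.3, with day 6 = 144 h and day 21 = 504 h). They fall on four visit days: three on day 0, one on day 1, three on day 6 and one on day 21. Alpha is 0.05 (section 8.2). Missing rates and correlations are assumptions.

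**1. What each test estimates.** Let d be the mean change from baseline common to both arms and b the extra change due to Beta-glucan.

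- Paired test in the treated arm: d + b.
- Time effect with all 15 pooled and no arm factor: d + (10/15)b = d + 0.67b.
- Time main effect with arm in the model and arms weighted equally: d + b/2.
- Arm-by-time: (d + b) − d = b.

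If b = 0, the first three still test d. Only the last isolates b, and section 8.2 does not name it.

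**2. Subjects left after complete-case deletion.** If a proportion m of k units is missing independently, a subject is complete with probability (1−m)^k. The expected number complete is 15 × (1−m)^k, or 5 × (1−m)^k for controls.

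| Missing unit | m | (1−m)^k | of 15 | of 5 controls |
|---|---|---|---|---|
| single samples, k = 8 | 2% | 0.851 | 12.8 | 4.3 |
| single samples, k = 8 | 5% | 0.663 | 10.0 | 3.3 |
| whole visit days, k = 4 | 2% | 0.922 | 13.8 | 4.6 |
| whole visit days, k = 4 | 5% | 0.815 | 12.2 | 4.1 |

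At 2%, the chance that all 15 are complete is 0.98^120 = 0.09 for independent samples and 0.98^60 = 0.30 for whole days.

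**3. Seven or eight time points.** 8 × 45 ml = 360 ml, so the blood volume fits eight draws. If seven time points are analysed, 0.98^7 = 0.868 leaves 13.0 of 15 and 0.95^7 = 0.698 leaves 10.5. The conclusion does not depend on which number applies.

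**4. Type I error of the arm-by-time F-test.** Simulation under no effect, 10 + 5 subjects, eight times, 20,000 runs per case, nominal 5%:

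| Assumed correlation | Uncorrected | Greenhouse-Geisser | Huynh-Feldt |
|---|---|---|---|
| Compound symmetry (epsilon 1) | 4.7% | 2.4% | 4.3% |
| Subject effect + serial part + noise (epsilon 0.89 to 0.67) | 5.9–7.6% | 2.9–3.6% | 5.2–5.6% |
| Pure serial decay, range 12 to 504 h (epsilon 0.53 to 0.30) | 9.0–13.3% | 4.0–4.8% | 5.3–5.6% |

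With seven times, the uncorrected figure is 5.2% under compound symmetry and 5.6–12.5% under the decaying patterns. With eight evenly spaced times and decay ranges of 72, 168 and 504 h it is 6.3%, 8.4% and 10.7%, against 12.4%, 13.0% and 13.3% with the protocol's spacing. Uneven spacing adds to the inflation but is not its only source.

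**The case against.** The strongest reply is that section 8.2 is a short outline and the details belong in an analysis plan that is not shown.

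- **Sphericity.** This reply succeeds. A reader might infer that the plan's F-test runs at 6–13% instead of 5%. The protocol does not say that the test will be uncorrected, it gives no correlation, and under compound symmetry the rate is about 5%. Nor does uneven spacing by itself invalidate an ANOVA that treats time as categories. It acts only through the correlation pattern.
- **Arm comparison.** A reader might also infer that the protocol rules out comparing the arms. It does not: a repeated-measures ANOVA can carry an arm factor. What stands is that section 8.2 chooses specific tests, all of them for change within subjects, and leaves the randomised contrast unnamed.
- **Missing samples.** A reader might take the loss of a third of the subjects as expected. That is only the 5% independent-sample case. Whole-day misses give a smaller loss, and the documents give no rate. Section 7.4.1 allows withdrawal after a protocol violation, so a subject who misses a visit might be replaced under section 7.5. That does not clearly cover a single failed assay. Bias from samples missed because of poor tolerance is possible, but nothing in the documents indicates it.
- **Stakes.** This is a pilot without a power calculation (section 4.4), and the synopsis calls the analysis descriptive. That limits the weight of the point. Section 8.2 nevertheless sets a significance threshold, so its tests will be read as tests.

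**Conclusion.** The point holds as a modest, inexpensive improvement. As worded, section 8.2 can be carried out in full without using the randomised controls, and a time effect shared by both arms could then be credited to Beta-glucan. This follows from the text and needs no numerical assumption.

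The complete-case loss is a property of the named method. Its size rests on an assumed 2–5% missing: 12.8 to 10.0 complete subjects of 15 if samples fail independently, 13.8 to 12.2 if whole visit days are missed. Type I inflation is conditional on both an uncorrected test and a decaying correlation, so it is only a reason to state the correction if ANOVA is kept. The seven listed immunological time points and the eight draws are a separate inconsistency that leaves these conclusions unchanged.

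**What to change.** Replace the ANOVA sentence in section 8.2 with a linear mixed model for repeated measures that uses all available samples. Include arm, time (categorical), arm-by-time and the baseline value, with a simple covariance structure suited to 15 subjects and small-sample degrees of freedom. Make arm-by-time the tested comparison, and report the arm difference at each time with a 95% confidence interval. These differences answer the immediate, repeated-intake and prolonged-effect questions in section 7.3 directly.

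One detail needs care. If baseline is a covariate and only later samples are outcomes, a constant shift sits in the arm term. In that case test arm and arm-by-time jointly. If baseline is kept as one of the time levels, arm-by-time alone is the test.

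If ANOVA is retained, name arm-by-time as the tested term, state an epsilon correction and give a rule for missed samples. Separately, reconcile the seven immunological time points in section 7.3.2 with the eight draws in sections 7.3, 7.3.2 and 7.3.3.

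The cost is a few sentences, slightly more analysis work and reliance on a covariance assumption in a small sample. The simulations above cover the ANOVA only, so the mixed model's error rate with 10 and 5 subjects should be checked, along with whether the named software release offers the chosen degrees of freedom.

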Drugs and dosage Commercial available Beta-glucan derived from bakers yeast (S. Cerevisiae): Glucan #300® produced by Transferpoint, Columbia, United States. 2 capsules of 500mg Glucan #300®, daily, for seven days.

Route of administration Oral administration.

Procedures 10 Healthy volunteers will take Beta-glucan 1000 mg daily for seven days, 5 other healthy volunteers will serve as a control group and do not have to take Beta-glucan. The *ex-vivo* responsiveness of leukocytes to various inflammatory stimuli, peripheral blood mRNA expression of genes related to the immune response, epigenetic modifications, the leukocyte capacity to phagocytose and kill the fungal pathogen *Candida albicans*, blood levels of Beta-glucan, and faecal microbiota will be analyzed on different timepoints.

Statistical analysis Descriptive statistics.

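### The primary TNF-alpha outcome has no time point and no declared primary test, so the flat p<0.05 rule does not hold its false positive risk at 5%

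*Protocol*

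**What the plan says.** Section 7.1.1 states "The primary outcome measure is the TNF- α secretion by" LPS-stimulated PBMCs. The study synopsis and section 2 define the same outcome. None of the three gives a time.

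Section 7.3 sets the draws: "Before, and 3, 6, and 24 hours after the first Beta-glucan ingestion (day 0), before, and 3 and 6 hours after the 7th ingestion", and again on day 21. That is one baseline and seven later samples. Sections 7.3.1 and 7.3.3 agree, and 7.3.2 counts eight draws in its blood volume. The list of immunological sampling times in 7.3.2, however, leaves out the 24-hour sample and so gives six later times. Section 7.3 asks three separate questions of these samples: the immediate effect, any additive effect of repeated intake, and any prolonged effect at three weeks.

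Section 8.2 gives the analysis in three sentences. One covers pairwise testing: "For comparisons, paired Students t -tests or Willcoxon-tests for parametric and nonparametric data as appropriate will be used". Another deals with the time course and plans a single kind of model: "Changes over time will be analysed using ANOVA repeated measures". The third sets the threshold for all of it: "A p value <0.05 is considered significant". The section contains no ranking of tests, no adjustment and no exploratory label.

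The secondary endpoints in 7.1.2 list seven cytokines and six stimuli. Section 7.3.2 adds a second cell preparation ("Method: PBMC and monocyte stimulation").

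**The concern.** A primary outcome protects against selective claims only if it is settled in advance which result decides it. Here any of seven changes from baseline, or the ANOVA, could cross 0.05 and be reported as a significant effect on the primary outcome, and each would comply with 8.2 as written. The design is open-label (7.2), so blinding does not guard against choosing the time after the results are known.

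The same rule, without distinction, governs the cytokine panel. Section 12.2 says the study will have assessed the potential of Beta-glucan as an immune stimulant in humans and points towards adjunctive treatment of sepsis. A positive statement from this study is therefore meant to carry some weight.

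**Working it through.** The protocol states no power, sample-size or familywise error figure to reproduce. The one count that can be checked is the number of draws: 8 × 45 ml = 360 ml, as 7.3.2 says, so there are 8 − 1 = 7 post-baseline times.

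**Inputs**
- Threshold 0.05 per test (8.2); sidedness is not stated and is taken as two-sided.
- 10 treated and 5 control subjects (section 3).
- 7 post-baseline times (7.3), or 6 on the list in 7.3.2.
- 7 cytokines and 6 stimuli (7.1.2); 2 cell preparations (7.3.2).
- Correlations are not given and are varied as assumptions.

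**Primary outcome, one paired test per time, no true effect**
- Independent tests: 1 − 0.95^7 = 30.2%. With six times: 1 − 0.95^6 = 26.5%.
- Changes that share one baseline correlate 0.5 when the raw values are equally correlated over time. Simulated with n = 10: about 24%.
- Changes correlated 0.7 over time: about 20%. Correlated 0.9: about 12%.

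**Primary outcome, other readings of 8.2** (simulated, n = 10, 8 times, equal correlation)
- One omnibus ANOVA as the only test: 5.0%.
- Paired tests only after a significant ANOVA: 3.8%.
- Either route may win: about 25%.

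**Cytokine panel, including the primary outcome**
- Six times, one preparation: 7 × 6 × 6 = 252 contrasts; 252 × 0.05 = 12.6 false positives expected.
- Seven times: 7 × 6 × 7 = 294; 14.7 expected.
- Both preparations: 2 × 294 = 588; 29.4 expected.
- One ANOVA per cytokine-stimulus pair: 7 × 6 = 42 tests; 2.1 expected; 1 − 0.95^42 = 88.4% for at least one if independent.

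Chance of at least one false positive among the 294 contrasts, simulated with n = 10:

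| Correlation between outcomes | Changes correlated 0.5 over time | Changes correlated 0.9 over time |
|---|---|---|
| 0.5 | 99.5% | 90% |
| 0.7 | 95% | 73% |
| 0.9 | 71% | 42% |

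**Power of a between-arm test.** For an unadjusted two-sample t-test at one time, 10 versus 5, the noncentrality is d × √(10 × 5 / 15) = 1.83d on 13 degrees of freedom. Power of 80% at two-sided 0.05 needs d of about 1.7 SD.

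**The case against.** The strongest reply is that 8.2 does plan a time analysis. One repeated-measures ANOVA of the primary outcome holds about 5%, and paired tests run only after it would be conservative. On that reading the 24% belongs to a procedure the protocol does not spell out. This stands in part: the figure is conditional on the paired tests being run at each time. But 8.2 neither names the ANOVA as the primary test nor makes it a gate, so the 24% route is permitted by the text.

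A second reply is that this is a 15-person pilot without a power calculation, and that time points and multiplicity rules may sit in a statistical analysis plan. Unadjusted testing is acceptable in a pilot when it is labelled exploratory. Section 8.2 carries no such label and sets a significance rule of its own, which a later document would have to override. The point therefore does not rest on silence.

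A reader might infer more than the document supports:
- **A near-certain false positive on the primary outcome.** Not so; the risk there is about 12% to 30%, or 5% under a single declared test.
- **Hundreds of planned contrasts.** The counts are maxima. Nothing says that every cytokine is tested for every stimulus, preparation and time.
- **Hundreds of false positive genes.** Section 8.2 does not name transcriptomic, epigenetic or microbiota data, 7.1.2 frames the transcriptome as pathways, and no gene count is given. Coverage by the 0.05 rule would be an inference.
- **A contradiction with the synopsis line "Statistical analysis Descriptive statistics".** Section 8.2, which holds the tests and the threshold, bears that same title, so the synopsis may simply repeat it.

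**Conclusion.** The concern holds in this form: as written, 8.2 lets the primary outcome be called significant at any of seven times or through an ANOVA, with no declared primary test. If the paired tests are used at each time, the false positive risk is about 24% rather than 5%. That figure assumes no true effect, n = 10, a shared baseline and equal correlation over time; the range under other assumed correlations is about 12% to 30%.

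For the cytokine panel, at least one false positive is very likely under the null. It becomes much less likely only with very high correlation, down to 42% in the most correlated case tried. The conclusion does not need the omics data or the synopsis line.

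This affects what may be called significant, not the conduct of the study, and wording alone can cure it.

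**What to change.** 1. In 7.1.1 and 8.2, name a single primary test before data are seen: either LPS-induced TNF-alpha in PBMCs at one stated time, or one ANOVA term. The arm-by-time term is preferable to a within-arm time effect because a control arm exists. Day 6 before the seventh intake is one defensible time point, not the only one.
2. Limit the p<0.05 rule to that test. Report all other times, stimuli and cytokines as exploratory estimates with 95% confidence intervals.
3. State that any feature-level testing of transcriptomic, epigenetic or microbiota data uses a false discovery rate.
4. Reconcile the sampling list in 7.3.2 with 7.3 on whether the 24-hour sample belongs to the immunological analysis.

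The cost is protocol wording. The downside is that the other times lose confirmatory status, and that a between-arm test at one time with 10 versus 5 subjects has 80% power only for a difference of about 1.7 SD, before any gain from baseline adjustment.
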